3.2 Subject Training

3.2.1 Self-Medication Education Program

West Park has a “Self-Medication Education Program” policy in place which seeks to establish independent medication SM capacity during the inpatient stay. Eligibility criteria for SME include a need to manage medications independently at home; stabilized on medication, as per

pharmacist/physician discretion; and mild-moderate cognitive/physical impairments, as per OT assessment. To determine SME eligibility, an OT and pharmacist completes the Interprofessional Screening for Self Medication Readiness (Appendix B) to determine self-management capacity. Eligible patients then receive training by an OT, followed by a 5-day self-medication performance assessment (Appendix C) by an RN prior to discharge. Following discharge, these patients are often referred to receive 24 OT outpatient therapy sessions for 3-months, on average.

CapitalCare will adopt the West Park “Self-Medication Education Program” program and documentation for purposes of this study. To determine SME eligibility, an OT, Pharmacist, or RN will complete applicable portions of the Interprofessional Screening for Self Medication Readiness (Appendix B) to determine self-management capacity. Eligible clients then will receive training by an OT, followed by a 5-day self-medication performance assessment (Appendix C) by an RN.

3.2.2 Orientation to KARIE

Patients randomly assigned to receive SME+K will undergo Screening for Self Medication Readiness (Appendix A) to determine self-management capacity, will receive SME by an OT, followed by a 5-day self-medication performance assessment (Appendix B) by an RN prior to discharge, as described above (see “Self-Medication Program”). In addition, this group will receive orientation to the KARIE Automated Medication Delivery Device. Karie orientation will be integrated into SME and delivered by the study OT, [name].

For purposes of this evaluation of the AceAge medication dispensing device, the SME and recruitment strategy will provide for: 1) standardized eligibility assessment, training, and performance evaluation of SM capacity for experimental and control subjects, 2) introduction to the AceAge device in the inpatient setting for experimental subjects, and 3) standardized medication adherence assessment during the 3-month outpatient follow-up period.

3.3 Apparatus

3.3.1 KARIE

The KARIE device delivers medication with the right dose at the right time, but it also monitors medication adherence, sends reminder alarms and produces timely adherence and side effects reports for physician review. The KARIE device can receive customized messages from health care providers; for instance, the patient can be asked about side effect(s) and/or the efficiency of the prescribed medication. Capture of this critical information will improve the clinical team's capacity to optimize the pharmacological treatment of chronic diseases, to assist in managing polypharmacy and to detect earlier medication related problems allowing them to intervene quickly to prevent the need for physician consultations, ER visits and/or hospitalizations. The KARIE device uses the multi-dose pouch packaging that pre-organizes drugs specific to the patient. Information on the package is read by KARIE to automatically schedule medication dispense and notification times. The device is simple with a single load action and a single button. In addition, it has communication capabilities such that if a patient misses a dose dispense, a notification is sent to a family member or caregiver who can then remind the patient. The device can also produce reports for physicians regarding medication adherence, side effects, chronic disease control, and non-prescription medication use, so they can better manage chronic disease care in patients with multi-morbidity. The KARIE device works as follows:

1. Loading Medication:
 - Patient receives their medication pre-organized in a cartridge from their pharmacist;
 - The patient (or their informal caregiver) inserts the cartridge in the backside of the device;
 - The medication schedule is automatically loaded via 2D barcode; and
 - Device is ready to dispense.
2. Daily Use:
 - Device notifies the patient when it is time for each medication through an audible noise and visual light;

- Patient presses button to dispense the specific medication for that point in time;
- The device dispenses the correct medication and adherence data is collected
- Patient takes the medication and adverse events in time can be recorded; and
- Dose dispense times are logged by the device.

3. Forgetting Medication:

- Device notifies the patient when it is time for each medication through and audible noise and visual light; and
- If patient does not take medication for 40 minutes or at customized times, a notification is sent.

4. Patient-reported Outcomes:

- Real-time data collection at time of dose dispense;
- Customizable questions for study or medication relevancy; and
- Create accurate, enriched datasets when combined with user log data.

3.3.2 Medication Adherence Log

Study participants in the SME and SME+K groups will be provided with a medication adherence log. Participants will be asked to complete a log entry with every scheduled medication dispense time. Participants will be asked to record the medications and the time they were taken. If a medication was missed, participants will be asked to leave the entry blank for that particular time.

3.4 Data Collection

The study RA will contact each study participant to arrange a data collection session within 24-48 hours prior to discharge. Data collection will include those scales identified in Outcome Measures above. Following discharge to the community, RAs will contact study participants via telephone on a bi-weekly basis to enquire about any missed medications. During these telephone contacts the RA and study participant will review the medication adherence log for the previous 2 weeks.

Data collection will be repeated at 3-months post-discharge. The RA will contact the participant 1-2 weeks prior to completion of the 3-month intervention period to schedule in in-home visit where post-intervention data collection will take place. In addition, the RA will collect participant medication adherence log.

4 ANALYSIS

A 2x2 repeated measures analysis of variance will be conducted to test for significant between-groups differences at baseline and post-intervention, as well as within-groups comparisons from baseline to post-intervention. An intention-to-treat analysis using last-observation-carried-forward will be used to account for subjects who do not complete the 3-month intervention.

We will follow qualitative analysis methods established in healthcare research: simple content analysis of survey results and inductive thematic analysis of interview results. With regard to survey and interview data, we will also conduct descriptive statistics across intervention and control baseline measures to assess the variability within measures, and bivariate association between measures of adherence. Results will be interpreted cautiously rather than considered definitive.

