2 METHODS

2.1 Design

This study will utilize a multi-site randomized controlled trial design. One week prior to discharge from inpatient rehab, consenting patients will be randomly assigned to receive medication self-management education only (SME) or medication self-management education + KARIE (SME+K).

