3.1 Recruitment

Potential West Park study participants will initially be identified by clinical staff referring to SME. Apparently appropriate subjects will be informed of the study by a member of their care team and, if interested, identified as wishing to receive additional information about the study during their initial meeting with the SME OT. The OT will briefly explain the nature of the study and request consent for the study research assistant (RA) to contact the patient to provide additional details of the study objective and procedures. The RA will arrange to meet with patient expressing an interest in participating in the study to obtain written consent (see Appendix A) and conduct baseline measures. The OT and pharmacist delivering the SMP will be blinded to group assignment.

Potential CapitalCare study participants will be identified by the research team Occupational Therapist. The Occupational Therapist (OT) will share this information with the CapitalCare research assistant (RA) who will be in regular contact. The RA will acquire consent and collect baseline data from the client (see inclusion criteria and measures for definitions).

The study RA, who will be blind to the assignment of the client to either intervention or control group, will approach the potential participant to explain the study, its purpose and aims to obtain informed consent for the study. As far as possible to maintain, the researcher will be unaware of the designation of the client to the Karie or control group.

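### Section 4 does not say which test is the treatment effect and uses no baseline covariate; baseline timing must be settled before adjustment is adopted

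*Combined protocol and SAP*

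**What the plan says.** **Analysis (Section 4).** The quantitative plan is that "A 2x2 repeated measures analysis of variance will be conducted to test for significant between-groups differences at baseline and post-intervention". The same sentence then extends the testing to change inside each arm: "as well as within-groups comparisons from baseline to post-intervention". Participants who do not complete are handled by intention to treat with last observation carried forward. No contrast is designated as the treatment effect, group-by-time is not named, and there is no baseline or site covariate.

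**Timing of randomisation (Section 2.1).** "One week prior to discharge from inpatient rehab, consenting patients will be randomly assigned".

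**Timing of baseline.** Section 3.1 has the West Park research assistant (RA) meet the patient to "obtain written consent (see Appendix A) and conduct baseline measures". For CapitalCare, "The RA will acquire consent and collect baseline data from the client". It adds: "The study RA, who will be blind to the assignment of the client to either intervention or control group, will approach the potential participant". It does not say which scales make up these baseline measures. Section 3.4 does tie the Section 2.3 scales to a session: 24-48 hours before discharge, repeated 3 months after discharge.

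**Device exposure before discharge (Section 3.2.2).** "Karie orientation will be integrated into SME and delivered by the study OT". In the device arm this training is "followed by a 5-day self-medication performance assessment (Appendix B) by an RN prior to discharge".

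**The concern.** Section 4 puts three kinds of comparison side by side, and they do not answer the same question.

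- A between-arm p-value at baseline says nothing about the device.
- A within-arm change mixes the device with discharge, training and time.
- Only the post-intervention between-arm test, and the group-by-time term that a 2x2 repeated-measures ANOVA produces, address the device.

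Those last two can disagree, and no rule says which one is the result. Neither makes the best use of baseline: the 3-month test ignores it, and group-by-time uses it only through a change score.

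The obvious remedy is to adjust for baseline, but that is safe only if baseline precedes allocation. If the scales are first given after device orientation, part of the device's effect may already be in the baseline score, and adjusting for it or subtracting it removes that part.

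**Working it through.** **1. The plan's own figures.** West Park: 25 × 3 × 0.20 × 10 = 150, or 75 per arm. With 80% compliance, 75 / 0.80 = 93.75, so 94 per arm. Both reproduce. CapitalCare adds 75 per arm, giving 75 + 75 = 150 per arm pooled. Section 2.2 states no power, effect size, SD or correlation, so there is no power calculation to reproduce.

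**2. Sequence at West Park, in days before discharge.**

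| Event | Days before discharge | Section |
|---|---|---|
| Consent and baseline measures (scales not named) | 7 or more, since those randomised have consented | 3.1, 2.1 |
| Randomisation | 7 | 2.1 |
| Training with device orientation | ends at least 5 days before | 3.2.2 |
| 5-day performance assessment | completed before discharge | 3.2.2 |
| Session with the outcome scales | 1 to 2 | 3.4 |

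The Section 3.4 session therefore falls 7 − 2 = 5 to 7 − 1 = 6 days after randomisation, and after orientation. CHOICE clients already live at home, so a time counted back from discharge defines neither their randomisation nor their scale session.

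**3. Precision with a pre-randomisation baseline.** Let ρ be the baseline to 3-month correlation (assumed; not in the documents), with complete data and equal variances at both visits. Variance per participant in units of σ²: 3-month-only 1; group-by-time 2(1 − ρ); ANCOVA 1 − ρ².

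Power = Φ(δ / √(2v/150) − 1.96), with v the variance above, two-sided 5% (assumed) and δ = 0.30 SD (assumed, the same at every ρ). For example, at ρ = 0.5 ANCOVA gives 0.30 / √(2 × 0.75/150) − 1.96 = 3.00 − 1.96 = 1.04, or 85%.

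| ρ | ANCOVA variance ÷ 3-month-only | ANCOVA variance ÷ group-by-time | Power: ANCOVA | 3-month-only | Group-by-time |
|---|---|---|---|---|---|
| 0.1 | 0.99 | 0.55 | 74% | 74% | 49% |
| 0.2 | 0.96 | 0.60 | 76% | 74% | 54% |
| 0.3 | 0.91 | 0.65 | 78% | 74% | 59% |
| 0.5 | 0.75 | 0.75 | 85% | 74% | 74% |
| 0.7 | 0.51 | 0.85 | 95% | 74% | 92% |

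**4. With carry-forward.** The 20% loss applies to the number enrolled, not to the 75 who are meant to remain. That is 94 + 75 = 169 per arm, or 94 + 94 = 188 if CapitalCare is inflated too (assumption). Assume that 20% in each arm carry baseline forward. The mean effect becomes 0.8δ and the correlation 0.2 + 0.8ρ. At ρ = 0.5 the correlation is 0.60; with δ = 0.2802 SD (assumed) the effect is 0.224.

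| Per arm | ANCOVA | Group-by-time | 3-month-only |
|---|---|---|---|
| 169 | 73% | 63% | 54% |
| 188 | 78% | 68% | 58% |

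**5. If baseline follows orientation.** Suppose orientation has already shifted the device arm's baseline by b (assumed), and the true 3-month effect is 0.30 SD. Expected estimates: 3-month-only 0.30; ANCOVA 0.30 − ρb; group-by-time 0.30 − b.

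| b | 3-month-only | ANCOVA at ρ 0.3/0.5/0.7 | Group-by-time |
|---|---|---|---|
| 0.1 SD | 0.30 | 0.27/0.25/0.23 | 0.20 |
| 0.2 SD | 0.30 | 0.24/0.20/0.16 | 0.10 |

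At b = 0.2, simulation (10,000 trials per scenario) gave ANCOVA 59/51/47% power against 73-74% for 3-month-only.

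**6. Site term.** Simulated with two equal sites, 1:1 allocation within site and the same site shift at both visits. At an assumed 0.5 SD gap between sites, adding site to ANCOVA gained 0.9/0.5/0.2 power points at ρ 0.3/0.5/0.7; at 1 SD, about 3/2/1 points.

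**The case against.** **The precision argument rests on a baseline that the plan may not have.** This stands. Section 3.4 is the only place that ties the outcome scales to a session, and on the West Park sequence that session follows allocation. Adjustment adopted without fixing the timing could do harm (step 5). A reader might go further and infer that baseline is certainly post-randomisation. The documents do not support that either. Section 3.1 places baseline measures at the consent meeting, and an RA unaware of allocation at that point fits a baseline taken before it. RA blinding would not, however, protect a patient-reported score from the effect of orientation.

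**Section 4 does name a post-intervention between-arm test.** True. It would be wrong to infer that the plan lacks a valid comparison, or that within-arm change is its intended result. What is missing is the statement of which result counts. Against that named test the gain may be negligible. Training at West Park aims to change self-medication capacity, and taking the scales before it could lower ρ. The large gains at low ρ are over group-by-time, which Section 4 never names.

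**This is a usability and feasibility study.** Adherence is a secondary objective in Section 2.3, and Section 4 promises cautious interpretation. That limits the stakes, but caution in interpretation does not select a contrast.

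**Conclusion.** The point holds as a recommended improvement, not as a finding that the planned analysis is invalid. Two things are established from the text: Section 4 leaves the treatment-effect contrast undesignated, and Sections 2.1, 3.1, 3.2.2 and 3.4 do not agree on whether the scales precede allocation.

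Given a pre-randomisation baseline, ANCOVA is, in large samples with equal variances, never less precise than either alternative. It ties with the 3-month test at ρ = 0 and with group-by-time at ρ = 1. How much it gains depends on a correlation that the documents do not give: from almost nothing over the 3-month test at ρ 0.1-0.2 to 21 power points (95% against 74%) at ρ 0.7. The effect size, the orientation shift and the site gap are also assumptions. Confidence in the size is therefore medium.

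Two limits apply. One adjusted contrast settles the choice of test within each scale, but it does not choose a primary scale among the five concerned (self-efficacy and the four self-report adherence measures). It also leaves the last-observation-carried-forward rule unresolved.

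**What to change.** 1. Reconcile Sections 2.1, 3.1 and 3.4 so that the scales are given before randomisation at both sites, and state when baseline and randomisation occur for CHOICE clients.

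2. Replace the first sentence of Section 4 with: *For each scale measured in both arms at baseline and 3 months, the treatment effect is the SME+K minus SME difference at 3 months, estimated by ANCOVA with arm, pre-randomisation baseline score and site (West Park or CapitalCare), with 95% CI. Baseline values and within-arm changes are reported descriptively, without p-values.*

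3. If the scales cannot be given before randomisation, designate the 3-month difference with arm and site only, without the baseline score.

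Device-recorded adherence, device satisfaction and the baseline-only beliefs questionnaire stay outside this model. The site term is worth including because the trial has two sites, but little precision should be expected from it.

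**Cost.** Free (analysis wording only) if the scales are already given at the consent meeting. Otherwise cheap: one RA session moves from just before discharge to before randomisation. No participants, visits or instruments are added.

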2.2 Participants

Study participants will include MSK, amputee, neuro rehabilitation and Geriatric Functional Enhancement Service (GFES) inpatients currently receiving care at West Park Healthcare Centre (Toronto) with a home transition plan following discharge. Inclusion criteria will include:

- need to manage medications independently at home;
- stabilized on medication, as per pharmacist/physician discretion; and
- mild-moderate cognitive/physical impairments, as per OT assessment
- Montreal Cognitive Assessment (MoCA) score not less than 16

It is anticipated that 20% of West Park patients will be eligible for SME and will consent to participation in the experimental trial. With 25 patients per unit and an average length of stay of 4-weeks on the MSK, amputee, neuro rehabilitation units, it is anticipated that a recruitment target of 75 experimental and 75 control subjects could be reached within a 10-month time frame (25 pts x 3 units x 20% x 10 months = 150 pts). These 150 patients from West Park will be randomly assigned to the SME (n=75) or SME+K (n=75) group. To meet this target an assumption of 80% compliance will be made. Therefore, up to 94 participants per experimental arm will be recruited. GFES length of stay is comparatively longer at roughly 12 weeks. It is expected that fewer patients will be recruited from GFES, but will contribute toward meeting the recruitment target.

One hundred fifty study participants will be recruited from the CapitalCare CHOICE programs (AB) which assist seniors to continue living independently and in their own home longer by managing all their health requirements. CapitalCare CHOICE clients attend one of three day centres, one to five days a week, and receive services which include ongoing medical, psychological, and social support. The total census for the CapitalCare CHOICE programs is 202 clients and enrollment varies. Initial recruitment will significantly predict how quickly the target of 75 experimental and 75 control subjects can be reached. If after the initial recruitment period suggests challenges meeting the target within the study timeframe, recruitment will be opened up to the CapitalCare Adult Day Program, Laurier House, Post-Acute, Sub-Acute, and Restorative Care clients at CapitalCare's other centres. The focus of these programs is to maintain client independence and autonomy while supporting personal care needs.

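### The planned group-by-time ANOVA has no site term, although 75:75 is set separately at two dissimilar sites; if the data are pooled, this costs a modest amount of precision

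*Combined protocol and SAP*

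**What the plan says.** Section 2.1 describes the design: "This study will utilize a multi-site randomized controlled trial design". Section 2.2 then gives each site its own numbers. For West Park: "These 150 patients from West Park will be randomly assigned to the SME (n=75) or SME+K (n=75) group". CapitalCare is to contribute a further 150, and its split is worded as a recruitment goal: "Initial recruitment will significantly predict how quickly the target of 75 experimental and 75 control subjects can be reached".

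The populations differ. West Park recruits rehabilitation inpatients who are about to go home. The CapitalCare CHOICE programmes serve seniors who already live at home and attend day centres.

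The only inferential model is in Section 4: "A 2x2 repeated measures analysis of variance will be conducted to test for significant between-groups differences at baseline and post-intervention". The same sentence adds within-group comparisons over the two time points, so the two factors are arm and time. Section 4 names no site factor, stratification variable or covariate. It does not say whether the model is fitted to both sites together or to each separately. The available text does not describe randomisation as stratified or blocked by site.

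**The concern.** With two arms and two times, the group-by-time test is the two-sample t-test on change scores. A constant site difference in level cancels from change, but a site difference in mean change does not. Without a site term, that difference is counted as patient-to-patient noise. In the between-group comparison at post-intervention nothing cancels, so the whole site difference in level enters the error.

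A site difference in change is plausible. Under Section 3.4 the pre-discharge baseline is taken 24 to 48 hours before leaving hospital, and follow-up is three months later at home. At West Park the comparison is therefore ward against home, often with outpatient therapy in between (Section 3.2.1). CHOICE clients are at home throughout.

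What is at stake is the width of the confidence intervals and the power of the arm comparison, on scales measured in both arms at both times. The plan states no power calculation, so it shows no margin to absorb a loss.

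**Working it through.** **The plan's own figures.** Section 2.2: 25 × 3 × 0.20 × 10 = 150 for West Park, or 75 per arm. With the 80% compliance assumption, 75 / 0.80 = 93.75, rounded up to 94 per arm. Both reproduce. The documents give no alpha, power, effect size or SD, so there is no power figure to reproduce.

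**Inputs**
- From Section 2.2: two sites, 75 per arm at each, so 150 per arm if pooled.
- Assumed: two-sided alpha of 5%; an arm effect of 0.3 within-site SD of change, for illustration only; D, the site difference in mean change in within-site SDs, from 0 to 1.0.

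**Formulas, arms balanced within site**
- Standard error with site in the model, in SD units: √(2/150) = 0.1155.
- Two equal sites whose mean change differs by D add D²/4 to the residual variance. The standard error reported without site is therefore multiplied by k = √(1 + D²/4).
- The arm difference itself still varies with standard error 0.1155, because equal arms within site cancel the site difference.
- Actual type I error without site: 2 × [1 − Φ(1.96k)].
- Power without site: Φ(0.3 × √75 − 1.96k), where 0.3 × √75 = 2.598.

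| D | k | SE without site | Type I error | Power |
|---|---|---|---|---|
| 0 | 1.000 | 0.1155 | 5.0% | 73.8% |
| 0.2 | 1.005 | 0.1160 | 4.9% | 73.5% |
| 0.3 | 1.011 | 0.1168 | 4.75% | 73.1% |
| 0.5 | 1.031 | 0.1190 | 4.3% | 71.8% |
| 1.0 | 1.118 | 0.1291 | 2.8% | 65.8% |

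With site in the model, power is 73.8% and type I error 5% in every row.

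**Simulation, 300 patients, 75 per arm per site, 10,000 null trials per setting.** Without site, the mean reported standard error was 0.119 at D = 0.5 and 0.129 at D = 1.0, while the estimate actually varied with an SD of 0.115 in both. The null was rejected in 4.3% and 3.0% of trials. With site in the model, the mean standard error was 0.115 and rejection was 5.1% and 4.9%.

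**If allocation is not balanced within site.** Arms were permuted across all 300 patients. Without site, the test then held its level: 5.0% rejection at both D = 0.5 and D = 1.0. The unadjusted standard error is valid for that design, because chance site imbalance really does add variance. It is still wider than the adjusted one: 0.119 against 0.116 at D = 0.5, and 0.129 against 0.116 at D = 1.0.

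**Recruiting 94 instead of 75.** If West Park alone enrolled 94 per arm, its share would be 94/169 = 0.556. The variance term becomes 0.556 × 0.444 × D² = 0.247D² instead of 0.25D², and k at D = 1.0 is 1.117 instead of 1.118. The percentages barely move.

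**Post-intervention comparison.** The same formula applies, with D read as the site difference in mean score at that time, in within-site SDs of the score.

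**The case against.** **Balance within site is not stated as a rule.** A reader might infer that the planned test certainly has a type I error below 5% and a standard error that is too large. That needs allocation forced to balance within each site. Section 2.2 comes close for West Park, but CapitalCare's split is only a target tied to recruitment speed, and no stratification or blocking is described. This objection stands: the conservatism is conditional. The loss of precision is not, provided the data are pooled and the sites differ.

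**Pooling is not stated.** If the ANOVA were run separately at each site, no site variance would remain in the error. That is possible, but one stated ANOVA in a trial described as multi-site makes pooling the likelier reading.

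**The size is assumed.** A reader might take a large loss as established, since larger values of D give larger figures. Nothing in the documents supports a particular D. CapitalCare adopts the same education programme, West Park's outpatient therapy is only a frequent referral, and a difference in setting may show mainly in level, which cancels from change. Below about 0.3 SD the loss is negligible. This stands, and it is why the range starts at zero.

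**Not every measure is affected.** A reader might infer a loss on every scale. Section 2.3 collects the Beliefs About Medication questionnaire at baseline only, so it has no change score. The KARIE electronic data exist only in the arm that receives the device, so they allow no comparison between arms.

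**The consequences are mild.** There is no bias and no excess of false positives, the primary objective is usability and feasibility, and Section 4 promises cautious interpretation. This limits the weight of the point. It is no reason to leave site out, since adding it costs almost nothing.

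**Conclusion.** The point holds as a matter of precision. Section 4 omits site from the model although the trial sets its numbers site by site in two dissimilar populations. If the data are pooled, site differences in change, and in level at post-intervention, are left in the error term. The arm effect remains unbiased.

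The loss runs from nothing (D = 0), through 3% on the standard error and 2 points of power (D = 0.5), to 12% and 8 points (D = 1.0). The power figures assume 75 per arm per site, balance within site and a 0.3 SD effect. The documents supply neither D nor the effect size. Under within-site balance the test is also conservative; without it, the unadjusted analysis is valid but less precise than it could be. The conclusion covers only scales measured in both arms at both times. This is a free improvement of modest size.

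**What to change.** In Section 4, specify one pooled model per eligible outcome with arm, time, arm-by-time, site and site-by-time. For the group-by-time question this is equivalent to regressing change on arm and site. For the post-intervention comparison, include site in the same way. Report the site-adjusted arm effect as the result, and show the effects at West Park and CapitalCare descriptively beside it. In Section 2.1 or 2.2, state that randomisation is carried out within site, so that the analysis follows the allocation.

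The cost is a sentence in each place and one degree of freedom out of about 300 patients. Site is already known for every participant. Recruitment, data collection and conduct of the interventions do not change. If the sites turn out not to differ, almost nothing is lost.

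### The planned within-arm tests of self-reported adherence compare readings taken under different conditions, so a change from baseline to 3 months cannot be credited to KARIE or to SME.

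*Combined protocol and SAP*

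**What the plan says.** Section 4 specifies a 2x2 repeated measures ANOVA for between-group differences, "as well as within-groups comparisons from baseline to post-intervention". It makes no allowance for any difference in how the two readings are obtained. Non-completers are handled by last observation carried forward.

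Section 2.3 lists four self-report adherence measures: the Morisky scale, the Medication Adherence Questionnaire, the Brief Medication Questionnaire and a 7-day recall. The one objective measure comes from the KARIE device. It has no value before the device is in use and none in the SME arm, so a within-arm adherence test has to use self-report.

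**First reading.** Section 3.4 has the RA "arrange a data collection session within 24-48 hours prior to discharge". Section 3.1 could place it earlier for West Park, since the RA meets the patient "to obtain written consent (see Appendix A) and conduct baseline measures". Section 3.2.1 adds OT training and a 5-day performance assessment by a nurse before discharge. For CapitalCare, section 3.1 says only "The RA will acquire consent and collect baseline data from the client".

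**Between the readings.** Section 3.3.2, for both arms: "Participants will be asked to complete a log entry with every scheduled medication dispense time". Section 3.4: "Following discharge to the community, RAs will contact study participants via telephone on a bi-weekly basis to enquire about any missed medications". On those calls "the RA and study participant will review the medication adherence log for the previous 2 weeks".

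**Second reading.** The scales are repeated at an in-home visit at 3 months. "In addition, the RA will collect participant medication adherence log".

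**The concern.** A before-after test within one arm has no control for anything else that changes between the readings. Here the plan itself changes several things. A West Park patient first answers as an inpatient in a supervised self-medication programme. The same patient answers again at home, alone with the medicines, after months of recording each dose and being asked every two weeks what was missed.

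Any of these can move the score. Closer attention to missed doses may lead to more being reported. Repeated enquiry may improve reported adherence, or real adherence. Leaving the ward may lower adherence whatever the arm. A significant within-arm change could then be read as a KARIE benefit, or as deterioration under SME, when it is neither. Equally, a real KARIE gain could be hidden.

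**Working it through.** **The plan's own figures.** Section 2.2 gives recruitment arithmetic only, and it reproduces: 25 x 3 x 0.20 x 10 = 150, and 75/0.8 = 93.75, rounded up to 94 per arm. There is no alpha, SD, effect size or correlation. Sample sizes used below are 75 per arm (one site) and 150 per arm (both sites).

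**Conditions side by side (West Park).**

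| | Baseline | 3 months |
|---|---|---|
| Setting | inpatient | home |
| Supervision | SME training, 5-day nurse assessment | none described at dosing |
| RA missed-dose calls so far | none; they start after discharge | floor(13/2) = 6 |
| Dose log | start date not given; the calls place it in follow-up | about three months |

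Under section 3.4, a 7-day recall taken 1-2 days before discharge reaches back at most 9 days. With an average stay of 4 weeks (longer on GFES), those are normally inpatient days.

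**Illustration 1: standardised shift (assumed inputs).** Behaviour does not change. The score shifts by d SD because of conditions alone. The correlation between readings is r, so the SD of change is sqrt(2(1-r)). The test is a two-sided 5% paired t test with noncentrality d x sqrt(n)/sqrt(2(1-r)). For d = 0.2 and n = 75:

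- r = 0.3: 0.2 x 8.66/1.183 = 1.46, rejection 30%
- r = 0.5: 0.2 x 8.66/1 = 1.73, rejection 40%
- r = 0.7: 0.2 x 8.66/0.775 = 2.24, rejection 60%

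Range over r = 0.3 to 0.7:

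| d | 75 per arm | 150 per arm |
|---|---|---|
| 0.1 | 11-20% | 18-35% |
| 0.2 | 30-60% | 54-88% |
| 0.3 | 58-91% | 87-100% |
| 0.5 | 95-100% | about 100% |

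The test is two-sided, so the rates are the same for an upward or a downward shift.

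**Illustration 2: percentage of doses (assumed inputs).** This fits the 7-day recall at most. The true missed-dose rate is constant at 10% and the SD of change is 10 points. Apparent change = missed rate x change in the share of missed doses reported.

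- 70% to 80% reported: 10% x 0.10 = 1 point, rejection 14% at n = 75
- 60% to 80%: 10% x 0.20 = 2 points, rejection 40% at n = 75 and 68% at n = 150
- 50% to 90%: 10% x 0.40 = 4 points, rejection 93% at n = 75

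**Group-by-time contrast.** With the same 0.2 SD shift in both arms and r = 0.5, 20,000 simulated trials reject in 4.8% (n = 75) and 5.1% (n = 150). If the shift differs between arms by 0.2 SD, rejection is 18-35% at n = 75 for r = 0.7 down to 0.3 read in reverse, that is, 18% at r = 0.3 and 35% at r = 0.7.

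**Last observation carried forward.** A non-completer with only a baseline value gets zero change. Suppose 20% are carried forward in the 2-point case. The mean change becomes 0.8 x 2 = 1.6, the variance 0.8 x 100 + 0.8 x 0.2 x 4 = 80.64, and the SD 8.98. The standardised change falls from 2/10 = 0.20 to 1.6/8.98 = 0.18. Simulated rejection falls from 40% to about 33% (n = 75) and from 68% to about 58-59% (n = 150).

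**The case against.** The strongest reply is that this is a randomised trial, both arms receive the log and the calls, and the group-by-time term is the real test. Adherence is a secondary objective, and section 4 says its results will be read with caution. What is left is the usual weakness of uncontrolled before-after tests. Much of this stands: the between-arm contrast is protected to the extent that the effect is equal in both arms, and that limits the consequence. But section 4 still lists the within-group tests as planned analyses. The general caution neither names this problem nor withdraws them.

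A reader might infer several stronger points that the documents do not support:

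- **That unaided recall is compared with log-aided recall.** Nothing says the log is consulted when the 3-month scales are completed, and section 3.3.2 gives no date on which logging starts. The text supports no more than that participants have been primed by logging. Nor is the West Park baseline plain recall, since it is taken around a supervised inpatient programme.
- **That apparent adherence must fall, masking a KARIE gain.** Better detection of missed doses is one mechanism among several, and others act in the opposite direction.
- **That last observation carried forward makes it worse.** It dilutes the within-arm artefact, as shown above.
- **That the last call contaminates the 7-day recall.** Two-weekly calls through week 12 review weeks 11-12 at the latest, and a week-13 visit recalls week 13. No change to call timing is needed.
- **That the same holds equally at CapitalCare.** No discharge event is described for its clients, so neither the baseline of section 3.4 nor the start of the calls can be dated there.

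**Conclusion.** The concern holds for the within-arm tests of self-reported adherence and goes no further. At West Park, setting, supervision and reporting conditions differ between the two readings by design, so a within-arm change in either direction cannot be attributed to KARIE or to SME. This rests on the text of sections 3.2.1, 3.3.2, 3.4 and 4, plus the inference that logging belongs to follow-up. At CapitalCare it is plausible but not established.

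The size is unknown. The rejection rates depend entirely on assumed shifts, correlations and SDs. They show that even a modest shift could take a nominal 5% test far above 5%; they do not estimate what will happen in this trial. The randomised comparison survives if the effect is equal in both arms, which the documents neither show nor contradict.

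**What to change.** In section 4:

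1. Base the adherence conclusion on the between-arm contrast, either the group-by-time term or the 3-month difference adjusted for baseline.
2. Present within-group changes from baseline to 3 months descriptively, without significance tests.
3. State that setting and reporting conditions differ between the two readings.

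Optionally, in section 3.4, have the adherence scales completed at the 3-month visit before the log is reviewed or collected. This fixes the order of the visit but does not undo three months of logging, so it cannot replace the changes to section 4.

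The cost is a few sentences and the loss of within-arm p-values. No new data or visits are needed.
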